To address these inequities, our team launched Chama cha MamaToto (Chamas) in 2012 with the Government of Kenya [3,4] (Figure 1). The Chamas program is a group-based, community health volunteer (CHV)-led, peer-support and microfinance program that engages women in pregnancy and the first 1000 days of their child's life. Translated from Kiswahili as 'groups', Chamas are composed of 15-20 women, 2 elders, and 2 government-supported CHVs. Members attend 60–90 min sessions twice monthly. Each session focuses on health, social, and financial topics that have been developed locally and engages group learning through visual and participatory tools. The Year 1 health program focuses on prenatal and perinatal health (e.g., what to expect in prenatal care, benefits of facility delivery, tackling postpartum challenges, exclusive breastfeeding for 6 months, and completing infant immunizations). Years 2 and 3 focus on family planning, parenting skills to foster positive relationships with their children, and strategies to reduce harsh child punishment and alleviate parental stress. Women can decide to join Chamas at any year. Throughout all 3 years, women can engage in a microfinance component that enables them to sustainably finance health practices, enroll in health insurance, start businesses, or meet other family needs. Participation in the group's table-banking is optional so as not to deter women without financial means from joining Chamas.

Chamas aims to recruit the most disadvantaged women in rural and peri-urban communities who face complex and intersecting challenges. The investigators hypothesize that fostering a strong, community-based network through Chamas provides women with the peer support, knowledge, and financial capital that increases their ability to (1) access maternal, newborn, and child health (MNCH) services, (2) improve their socio-economic position, and (3) sustain long-term transformative change (Figure 1).

To test this theory of change, the investigators have carried out successive evaluations leveraging support from county governments and Grand Challenges Canada. The investigators found significant improvements in MNCH outcomes among Chama participants in both our prospective cohort study (2012-2013; n=337) [3] and cluster randomized controlled trial (RCT) (2017-2019; n=1,550) [4]. Chama participants were more likely to engage in behaviours

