2.3 Methodology

Study Timeline: See Figure 2.

Study Design: The investigators will use a mixed-methods strategy using quantitative and qualitative approaches, leveraging cohorts from our RCT completed in Trans-Nzoia County (2017-2019). The investigators have selected a mixed-methods approach based on our experience that it provides a pragmatic approach to exploring complex social processes. The investigators have drawn on best practices from intersectionality-informed mixed methods research to guide this proposal [11].

Study Site: This study will be carried out in Trans-Nzoia County, where the investigators have longstanding partnership in HIV and MNCH care, including Chama implementation (see *Memorandum of Understanding in Policy Documents*). Trans-Nzoia has a population of 990,341 with 489,107 women and 129,558 children under-five [12]. During the RCT, women were recruited from public health facilities linked to any of the 77 community units (CUs) in 4 sub-counties (Saboti, Kiminini, Cherangany, and Kwanza). These sub-counties primarily subsist on agriculture and livestock farming, with increasing numbers of agricultural and small businesses. Kitale (in Saboti sub-county) is urban, Kiminini is peri-urban, and Cherangany and Kwanza are rural.

Health outcomes in Trans-Nzoia vary between sub-counties but are poor overall. Only 56% of children are fully immunized at age 1, and 58% of women deliver in facilities. The infant mortality rate is 58 per 1,000 livebirths compared to a national average of 39 per 1,000 [13]. Only 29% of women use family planning compared to a national average of 58% [13].

Study Population:

- (1) Women from the RCT who participated in Chamas throughout the pandemic (n=142).
- (2) Women who left Chamas after Mar 12, 2020, the day the first case of COVID-19 was detected in Kenya (n=600).
- (3) Women whose communities were randomized to not implement Chamas during the RCT (n=728).
- (4) CHVs in communities who either did or did not have Chamas operating during the pandemic.
- (5) County health officials.
- (6) Fathers participating in Chama cha Babatoto.
- (7) Adolescent girls currently participating in Chamas adapted for adolescents (15 to 24 years of age; enrolment after Jan 2022).

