Our recently completed RCT [4] uniquely positions our team to provide fine-grained empirical data about women's experiences of the pandemic as the investigators have a robust research infrastructure and strong linkages with the communities that participated in the trial. Following the completion of the RCT, the investigators planned to scale-up the program throughout Trans-Nzoia. This scale-up was put on hold due to the pandemic. As a result, there are now multiple groups of women in communities that are well positioned to share to what extent participating in Chamas helped mitigate the effects of the pandemic and related restrictions. Further, the investigators have the ability to compare this to the experiences of those women in the community units where Chamas have not yet been implemented.

Quantitative Data Collection and Analysis: The investigators will quantify the impacts of the pandemic on economic status and health service utilization among women in Trans-Nzoia, focusing on the first 3 study cohorts described above: (1) women who participated in Chamas throughout the pandemic (n=142), (2) women who left Chamas during the pandemic (n=600), (3) women whose communities were randomized to not receive the Chamas intervention (n=748). Our primary outcome will be the change in the mean 2015 Kenya PPI score pre- and post-pandemic for the study participants. The PPI is calculated using a validated set of 10 simple, easy-to-answer questions and estimates the likelihood the participant is living below the national poverty line, or other internationally recognized poverty lines [14]. Each response is given a value, and the total value of all the answers is the participant's PPI score. The PPI "look-up table" for Kenya will then be used to convert the PPI score to a likelihood of the respondent's household being below a poverty line. The investigators will also compare the PPI at the post-pandemic period between three cohorts. The investigators have chosen this as our primary outcome because, from an equity perspective, poor MNCH outcomes are disproportionate across socioeconomic strata. Access to care is generally correlated with economic accessibility and women of lower socioeconomic status often encounter greater barriers to accessing high quality care [14, 16]. The investigators have also chosen this variable as it is meaningful to the county government.

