For women enrolled in our RCT (pre-pandemic), the baseline mean PPI score was 57 (SD = 21) for all women. Assuming a 0.5 correlation between pre- and post-pandemic PPI measures, the investigators require a total of 444 participants to detect a 5% (2.8 points) change in PPI scores at a significance level of 5% with 80% power. Based on our total recruitment in the RCT (n = 1,550), this should be highly achievable. Using the same standard deviation above, the investigators would need a minimum of 108 participants per cohort to detect an 8-point difference in post-pandemic PPI between the three cohorts. This sample size is highly feasible given the number of women currently within each cohort.

Our secondary outcomes include indicators relevant to MNCH and COVID-19: enrollment in the national health insurance scheme, number of ANC visits attended, facility delivery, maternal death, newborn death, infant death, exclusive breastfeeding, number of children fully immunized

at age 1, attitude towards harsh punishment of children, level of parental stress, COVID-19 infection, COVID-19 vaccination, and effects of COVID restrictions. These data were collected in December 2021 with 1,400 Chama participants across Western Kenya, including 626 from Trans-Nzoia, using an abbreviated version of the validated survey tool from our RCT. Here, the investigators will carry out this survey across the three previously described cohorts of women in early 2023 to understand the effects of Chama participation more fully on these outcomes and quantify the effects of differing levels of PPI and other identity factors on Chama participation and these outcomes.

To obtain the post-pandemic data for women who participated in Chamas, the program's Data Analyst will generate a list of eligible women organized by community unit. CHVs responsible for each unit will locate, obtain consent, and enroll women. Field officers in Trans-Nzoia will oversee 8 local college-level practicum students to work with CHVs in collecting survey data, with each student responsible for a single sub-county. Integrating mentorship of local students in project implementation has been foundational to our engagement in Trans-Nzoia and replicates the data collection model the investigators used successfully for our RCT.

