First, the investigators will summarize descriptive data for the PPI and MNCH characteristics pre- and post-pandemic, as well as by each of the three cohorts specified above. To assess the overall change in PPI post-pandemic the investigators will use a linear mixed effects model adjusted for relevant baseline covariates to estimate the mean difference in PPI from pre to post. Second, the investigators will assess the relationship between sociodemographic variables (e.g., PPI, education, age) and health outcomes (e.g., health insurance status, ANC visits). The investigators will do this both overall by time period as well as disaggregated by cohort by including interactions between sociodemographic variables and cohort group. Results will be presented as cohort specific estimates (e.g., odds ratios for binary outcomes) as well as predicted probabilities of health outcomes by group. All models will account for clustering of data by sub-county using random effects and, when available, the investigators will adjust for relevant sub-county-level indicators. Exploratory analysis will include correlation between outcomes (by group) and reported COVID-19 cases.

When comparing each of the three cohorts the investigators will consider several approaches to adjust for possible confounding, as those who remain in Chamas may differ from those who did not. Confounders will be identified based on expert input and previous literature and adjusted for using doubly robust methods for causal inference, such as combining inverse probability weighting and standard regression, or via targeted maximum likelihood estimation [17, 18]. Sensitivity analyses for unmeasured confounding will be conducted and the investigators may consider further sensitivity analyses to assess impact of possible selection biases depending on the level of follow-up achieved from the original cohort(s) [18].

Qualitative Data Collection and Analysis: While the quantitative dataset will provide information on the impact of COVID on health service utilization and economic status, the investigators will draw on a qualitative approach to put these findings in context and specifically explore gender dynamics as social processes. The investigators will conduct focus group discussions (FGDs)

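### Stayers and leavers are defined by membership over the whole pandemic but compared on events that may come before leaving, so a child death can itself place a woman among the leavers

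*Protocol*

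**What the plan says.** Protocol section 2.3, Study Population, defines cohort 1 as "Women from the RCT who participated in Chamas throughout the pandemic (n=142" and cohort 2 as "Women who left Chamas after Mar 12, 2020, the day the first case of COVID-19 was detected in Kenya (n=600". The quantitative part of Aim 2 repeats the second definition as "2) women who left Chamas during the pandemic (n=600". Both labels depend on what a woman did over the whole period, so they are settled only at its end.

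The secondary outcomes include "number of ANC visits attended, facility delivery, maternal death, newborn death, infant death, exclusive breastfeeding", and immunisation at age 1. For collection, "the investigators will carry out this survey across the three previously described cohorts of women in early 2023". The stated purpose is to learn how Chama participation affects these outcomes.

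The analysis text says the investigators will consider several approaches to "adjust for possible confounding, as those who remain in Chamas may differ from those who did not". It gives inverse probability weighting combined with regression, or targeted maximum likelihood, as examples. It adds sensitivity analyses for unmeasured confounding and, possibly, for selection bias depending on follow-up.

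Section 2.1 describes a programme that "engages women in pregnancy and the first 1000 days of their child's life".

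**The concern.** A cohort label fixed at the end of a period is used to compare events that happened within it. A woman who gave birth as a member in 2020 and left in 2022 is a leaver for that birth. This has two different consequences.

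- **Newborn and infant death.** The programme is built around the child, so a woman who loses hers has a plausible reason to stop attending. The outcome then comes before the exposure label and helps to determine it. Stayers are partly selected for not having had the event, and staying looks protective even if it does nothing.
- **Antenatal care, facility delivery, breastfeeding and immunisation.** There is no comparable reason for these to cause leaving. Care received while a member is credited to the leavers, which misclassifies exposure and blurs the contrasts of cohort 1 with 2 and of cohort 2 with 3.

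Weighting or targeted maximum likelihood on prior confounders balances causes of exposure that precede it. It does not correct a label that is a consequence of the outcome. The matter deserves attention because the bias for child death runs in the direction of the study's hypothesis, and the findings are meant to guide scale-up.

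**Working it through.** **Figures stated in the plan.** The protocol gives no number for this point. Its sample sizes concern PPI and do not bear on it. They do reproduce: (2.80 × 21/2.8)² = 442, or 444 with the t distribution, against 444 stated; and 2 × (21 × 2.80/8)² = 108.2 against 108 stated.

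**Inputs.** From section 2.3: S = 142 stayers, L = 600 leavers, infant mortality p = 0.058. Assumed: cohorts 1 and 2 together are all the women who were members on 12 March 2020; membership has no effect on death; one infant at risk per woman (relaxed below). The unknown is q, the share of women with an infant death who end up as leavers.

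**Formulas.** The cohort totals are held at 142 and 600.

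- N = 142 + 600 = 742; overall leaving = 600/742 = 80.9%
- Deaths D = 742 × 0.058 = 43.0
- Leaving rate in women without a death: q0 = (600 − Dq)/(742 − D)
- Null odds ratio, leavers v stayers = [q/(1 − q)] / [q0/(1 − q0)]

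For q = 0.90: q0 = (600 − 38.7)/(742 − 43.0) = 0.803, and the odds ratio is 9.00/4.08 = 2.21.

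| q | Leavers | Stayers | Null odds ratio |
|---|---|---|---|
| 80.9% (unrelated to death) | 34.8/600 = 5.8% | 8.2/142 = 5.8% | 1.00 |
| 85% | 36.6/600 = 6.1% | 6.5/142 = 4.5% | 1.36 |
| 90% | 38.7/600 = 6.5% | 4.3/142 = 3.0% | 2.21 |
| 95% | 40.9/600 = 6.8% | 2.2/142 = 1.5% | 4.75 |
| 100% | 43.0/600 = 7.2% | 0/142 = 0% | infinite |

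If q were below 80.9%, the odds ratio would fall below 1 and the bias would reverse.

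**Chance of a significant false result** (Fisher exact test at 5%, 1,000 simulations), by the share of women with an infant at risk in the period. The odds ratios change little with this share.

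| q | All women | Half | A quarter |
|---|---|---|---|
| 85% | 7.0% | 3.7% | 1.7% |
| 90% | 32.0% | 10.6% | 1.4% |
| 95% | 77.7% | 31.9% | 3.7% |
| 100% | 100% | 78.1% | 6.7% |

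**Does dating the events help?** A second simulation followed women monthly for 33 months, again with no true effect. A death triggered leaving in 0, 25, 50 or 75% of bereaved women who were still members. Grouping by the whole-period label gave odds ratios of 1.00, 1.40, 2.27 and 4.78. Assigning each death to membership at the time it occurred gave rate ratios of 0.99 to 1.03 in every scenario, including 100%. The rule proposed under the fix, status at birth, is not identical to this split by time. It shares the property that matters: exposure is settled before the death.

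With no triggered leaving at all, 33% of the leavers' deaths in this simulation still happened while they were members. That is misclassification without bias under the null, and it is the situation of the care outcomes.

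**The case against.** The strongest reply is that the protocol nowhere states that an event counts under the cohort label whenever it happened. It gives no index birth or outcome window, which a statistical analysis plan commonly supplies, and the survey form may already record dates of birth. The odds ratios it mentions relate sociodemographic variables to health outcomes within cohorts, so the form of a direct cohort comparison is open. The doubly robust methods are given only as examples. All this is fair, and a reader should not infer that a wrong attribution rule has been laid down. What remains is that the protocol does fix the cohorts by whole-period membership, fixes a survey across them to learn the effects of participation, and describes the problem only as confounding, unmeasured confounding and possible selection.

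Four stronger readings are tempting and are not supported.

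- **That care outcomes will look better among stayers with no true effect.** No route from antenatal visits, delivery place, breastfeeding or immunisation to leaving is described. Late labelling alone creates no difference under the null, and under a true benefit it dilutes the contrast of cohort 1 with 2.
- **That infant deaths did drive women out.** The protocol gives no reasons for leaving. The programme has three years of content, so completion may explain much of it, and peer support could keep bereaved women in.
- **That a large false effect is likely.** These women come from a 2017-2019 trial, and many index children were probably past infancy by March 2020. The number of later births is not given. With a quarter of women at risk, a significant false result is uncommon even in the extreme scenarios.
- **That maternal death shows the same bias by definition.** The outcome is listed, but the protocol does not say how it is ascertained or how a woman who died would be assigned to a cohort.

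**Conclusion.** The point holds in a limited form. For newborn and infant death, comparing the cohorts as defined lets the outcome determine the exposure label, and the planned adjustment for confounding does not address that. For the care outcomes the fault is exposure misclassification only.

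The size for infant death cannot be known from the protocol. The null odds ratio ranges from 1.0 to about 1.4, 2.2 and 4.75 as the share of bereaved women who leave goes from 81% to 85%, 90% and 95%. These figures rest on infant mortality of 58 per 1,000, cohorts of 142 and 600, and assumed leaving rates. Whether a false result would reach significance depends mainly on how many pandemic births there were.

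The affected outcomes are secondary. A reader might extend the point to the primary outcome, but the 2023 PPI is measured after the label is settled. Differences in who stayed are then a question of confounding, which the protocol recognises and plans for.

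**What to change.** Record the month of leaving and the month of each pandemic birth, from programme records or in the survey. The protocol does not say that either is collected. For dated event outcomes, classify the woman by Chama membership when the event window opened:

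- start of the pregnancy, for antenatal visits;
- the birth, for facility delivery, newborn and infant death, breastfeeding and immunisation.

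Fit the weights to that exposure. Keep the stay/leave cohorts for outcomes measured at the 2023 interview, such as PPI.

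The cost is modest: the added dates and a revised analysis rule. Exposure becomes specific to each birth, so there is no longer one fixed cohort variable for all outcomes and the weights must be respecified. Repeated births to one woman must be handled, and recalled leaving dates carry some error. Dates not asked for in the survey may be hard to recover later.

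### The only pre-pandemic PPI described is the RCT baseline from a 2017-2019 trial, so the primary pre-to-post change cannot be read as the effect of the pandemic alone

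*Protocol*

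**What the plan says.** All references are to Protocol section 2.3 (Methodology) unless stated otherwise.

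- **Primary outcome (Aim 2, quantitative part):** "Our primary outcome will be the change in the mean 2015 Kenya PPI score pre- and post-pandemic for the study participants". The paragraph presents this as quantifying what the pandemic did to economic status. It adds a comparison of the three cohorts on PPI after the pandemic.
- **Pre value:** the sample-size paragraph gives "For women enrolled in our RCT (pre-pandemic), the baseline mean PPI score was 57 (SD = 21) for all women". No other PPI from before the pandemic is described.
- **Source trial:** the study is "leveraging cohorts from our RCT completed in Trans-Nzoia County (2017-2019".
- **Start of the pandemic:** the Study Population list uses 12 March 2020. Cohort 1 stayed in Chamas throughout and cohort 2 left after that date, so both were in Chamas when the pandemic began.
- **Post value:** "Here, the investigators will carry out this survey across the three previously described cohorts of women in early 2023".
- **Analysis:** a mixed model with baseline covariates "to estimate the mean difference in PPI from pre to post".
- **Expected programme effect:** section 2.1 hypothesises that Chamas raises women's economic standing, and it makes microfinance available in all three programme years.

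**The concern.** A pre-to-post difference can be credited to an event only if the pre value sits close to that event, or if change before it is otherwise accounted for. Here the described pre value comes from the start of a trial that finished before the pandemic. Two components unrelated to COVID-19 can therefore enter the primary outcome:

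1. Ordinary change in PPI between enrolment and March 2020, in all three cohorts.
2. Any gain that Chamas produced before March 2020, in cohorts 1 and 2.

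The second component also enters the planned comparison of cohorts on post-pandemic PPI. If Chamas women were already better off in March 2020, they could be better off in 2023 without any protection during the pandemic. Mitigation is the study's central hypothesis, and section 2.2 says the findings will guide scale-up. The error could run either way: an earlier gain could be reported as resilience, or it could offset and hide a real pandemic loss.

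**Working it through.** **1. The plan's own figures.** Inputs: SD 21; "Assuming a 0.5 correlation between pre- and post-pandemic PPI measures"; target 2.8 points; 5% significance; 80% power.

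- SD of the change = 21 × √(2 × (1 − 0.5)) = 21.
- n = (21 × (1.960 + 0.842) / 2.8)² = 441.5, so 442 by the normal approximation. The two-sided paired t-test gives 444.
- The plan says "require a total of 444 participants to detect a 5% (2.8 points) change in PPI scores at a significance level of 5% with 80% power". This is reproduced.
- Cohort comparison: 2 × (21 × 2.802 / 8)² = 108.2 per cohort, against "minimum of 108 participants per cohort to detect an 8-point difference in post-pandemic PPI between the three cohorts". This agrees to rounding.

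The arithmetic is sound. What is in doubt is what the change measures.

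**2. Age of the baseline.** Enrolment dates are not given. Section 2.1 reports RCT results for antenatal visits and for immunisation at 12 months. I therefore assume entry in pregnancy and, with the trial ending in 2019, entry no later than about December 2018. The earliest assumed entry is January 2017, and I take the survey as February 2023.

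| Enrolment | Months to March 2020 | Months to survey | Share before the pandemic |
|---|---|---|---|
| January 2017 | 38 (3.2 years) | 73 | 38/73 = 52% |
| December 2018 | 15 (about 1.2 years) | 50 | 15/50 = 30% |

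Without the 12-month argument, using only the RCT end date (31 December 2019), the lower bound falls to 0.2 years.

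**3. Drift before March 2020 that alone gives 2.8 points.**

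- Early enrolment: 2.8 / (38/12) = 0.88 points per year.
- Late enrolment: 2.8 / (15/12) = 2.24 points per year. Counting days from 31 December 2018 gives 1.20 years and 2.3.

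**4. Earlier Chama gain that alone gives 2.8 points in the overall change.** Cohorts 1 and 2 total 142 + 600 = 742. Cohort 3 is given as 728 in one place and 748 in another, so the total is 1,470 or 1,490.

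- 2.8 / (742/1,470) = 5.5 points.
- 2.8 / (742/1,490) = 5.6 points.

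**5. How often a smaller drift would be declared a change.** Take no pandemic effect, no Chama gain and an assumed drift of 0.5 points per year before March 2020. The shift is 0.5 × 1.2 = 0.6 to 0.5 × 3.2 = 1.6 points. Treat women as independent. With SE = 21/√n, rejection probability = Φ(shift/SE − 1.96) + Φ(−shift/SE − 1.96).

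| n | SE | Shift 0.6 | Shift 1.6 |
|---|---|---|---|
| 444 | 0.997 | 0.09 | 0.36 |
| 1,470 | 0.548 | 0.20 | 0.83 |

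Enrolling more women makes a false attribution more likely, because the shift is a bias and does not shrink with n.

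**6. Whether anything in the plan removes it.** The December 2021 survey falls inside the pandemic, so it cannot supply a pre value. The primary model has no stated term for calendar time or time since enrolment. The doubly robust methods are aimed at confounding between cohorts, in particular differences between women who stayed and women who did not. They do not address change in PPI before March 2020.

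**The case against.** The strongest reply is that the protocol never says outright that the enrolment value is the pre value of the primary outcome. The baseline figure sits in a sample-size paragraph and supplies a planning mean and SD. The RCT may hold a later PPI, and the choice of record could be left to an analysis plan. This stands as a limit on certainty. It does not remove the point, because the same sentence labels the figure both baseline and pre-pandemic and no alternative is described. No later model can recover a PPI that was not recorded near March 2020.

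The plan also does not rest on the raw change alone. It adds covariate adjustment, sensitivity analyses for unmeasured confounding, an exploratory correlation with reported COVID-19 cases, and qualitative work. These give context but do not separate change before March 2020 from change after it.

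Three stronger readings are tempting and are not supported:

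- **That the plan tests mitigation by comparing change between cohorts.** It does not. The primary outcome is one overall change, and cohorts are compared on post-pandemic PPI. The planned interactions are between sociodemographic variables and cohort, for health outcomes.
- **That drift of about half a point a year is enough to give 2.8 points.** Spreading 2.8 points over all 50 to 73 months gives 0.67 to 0.46 per year, but 35 of those months follow March 2020. Drift confined to the earlier period must be about 0.9 to 2.2 per year.
- **That the baseline is known to be one to three years too old.** The enrolment dates are inferred.

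**Conclusion.** The point holds in limited form. As written, the plan would attribute to the pandemic a change that begins at the RCT baseline, the only earlier PPI it describes. On the assumed enrolment dates, about 1.2 to 3.2 years, or 30% to 52% of the interval, precede 12 March 2020. The overall change then includes earlier drift and, in cohorts 1 and 2, earlier programme gain. The post-pandemic cohort comparison includes that gain and so does not isolate mitigation.

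Drift of about 0.9 to 2.2 points per year, or a Chama gain of about 5.5 points, would alone reach the 2.8-point target. These figures show scale only: the protocol documents no PPI drift rate, no direction of drift and no Chama effect on PPI. The conclusion rests on the enrolment value being the pre value and on the inferred dates. A reader might go further and infer that a bias of this size is present, or that the sample size is wrong. The documents show neither.

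**What to change.** 1. Define the pre-pandemic PPI as each woman's last PPI recorded before 12 March 2020, which is the RCT end-of-follow-up value if one exists. Use it for the primary change and as the baseline adjustment in the post-pandemic cohort comparison. State its date.
2. If only the enrolment value exists, restate the primary outcome as change in PPI from RCT enrolment to 2023, and do not attribute it to the pandemic alone. State that post-pandemic cohort differences include any Chama effect from before the pandemic.

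Adding months from baseline to March 2020 as a main effect is not a substitute. With one pre and one post value per woman it shifts both levels and leaves the pre-to-post contrast essentially unchanged.

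The cost is protocol wording and the use of dates and any follow-up PPI already held from the RCT; no new visit is needed. The downside is a narrower primary claim if no later value exists. Even with a value close to March 2020, about 35 months of ordinary change up to the survey remain in the contrast and should be acknowledged.

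### Maternal death is a secondary outcome, but the only source described is a survey of the women themselves, and cohort 1 has zero deaths by definition

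*Protocol*

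**What the plan says.** All of this is in Protocol section 2.3 (Methodology).

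- **Outcome.** Under Aim 2, quantitative data collection and analysis, the secondary outcomes include "number of ANC visits attended, facility delivery, maternal death, newborn death, infant death, exclusive breastfeeding".
- **Earlier collection.** "These data were collected in December 2021 with 1,400 Chama participants across Western Kenya", of whom 626 were from Trans-Nzoia, using a shortened form of the RCT survey tool.
- **Planned collection.** The investigators will "carry out this survey across the three previously described cohorts of women in early 2023". One stated purpose is "to understand the effects of Chama participation more fully on these outcomes".
- **How women enter.** For women who took part in Chamas, a list of eligible women is drawn up by community unit, and then "CHVs responsible for each unit will locate, obtain consent, and enroll women".
- **Cohorts.** Cohort 1 is "Women from the RCT who participated in Chamas throughout the pandemic (n=142"). Cohort 2 is "Women who left Chamas after Mar 12, 2020" (n=600). Cohort 3 is women in communities randomized to no Chamas, given as 728 under Study Population and 748 under Aim 2.
- **Analysis.** Maternal, newborn and child health characteristics are to be summarised by period and by cohort. Cohort comparisons are to use doubly robust methods, and further sensitivity analyses for selection bias are optional.

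No proxy or next-of-kin interview, death register, facility or civil-registration linkage, or vital-status log is described for any cohort.

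**The concern.** A woman who has died cannot be located, give consent or answer a questionnaire. If the woman's own interview is the only route into the data, her death is never seen. The outcome then yields a zero that reflects who could be interviewed, not the risk.

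The definition of cohort 1 adds a second problem. A woman must survive the pandemic to have participated for the whole of it, and cohorts 2 and 3 carry no such condition. The protocol does not say how a woman who died while a Chama member is classed. If community health volunteers (CHVs) noted deaths while tracing, cohorts 2 and 3 could show deaths while cohort 1 could not. That is immortal-time bias in favour of the hypothesis under study.

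These are alternative scenarios: a zero in every cohort if deaths are not recorded, or a biased difference if they are. Either result could be presented to county decision-makers as evidence on whether Chamas protected women. Doubly robust adjustment and selection-bias analyses cannot restore deaths that were never recorded.

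**Working it through.** **The plan's own figures.** The protocol gives no event count, sample size or power for maternal death, so there is no such figure to reproduce. Its sample sizes for the Poverty Probability Index (PPI) do reproduce and are not in question:

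- PPI change: SD of the difference = 21 × √(2 × (1 − 0.5)) = 21. Then n = ((1.960 + 0.842) × 21 / 2.8)² ≈ 442, or 444 with the t distribution. Stated: 444.
- Cohort comparison, 8 points with SD 21: 109 per cohort. Stated: 108.

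**What can be observed.**

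| Situation | Cohort 1 | Cohort 2 | Cohort 3 |
|---|---|---|---|
| Survey only, as described | 0, whatever the risk | 0, whatever the risk | 0, whatever the risk |
| Deaths noted at tracing | 0, by definition | can exceed 0 | can exceed 0 |

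**Scale if every death were captured.** Inputs:

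- Maternal mortality ratios of 211 (global) and 533 (sub-Saharan Africa) per 100,000 live births, from section 2.1.
- Cohort sizes 142, 600 and 728 from Study Population; total 1,470.
- Share of women with one pandemic-era birth: not given in the protocol. Assumed range 25% to 100%.

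Expected deaths = n × share × ratio / 100,000.

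| Group | n | At 211 | At 533 |
|---|---|---|---|
| Cohort 1 | 142 | 0.07 to 0.30 | 0.19 to 0.76 |
| Cohort 2 | 600 | 0.32 to 1.27 | 0.80 to 3.20 |
| Cohort 3 | 728 | 0.38 to 1.54 | 0.97 to 3.88 |
| All | 1,470 | 0.78 to 3.10 | 1.96 to 7.84 |

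With 748 in cohort 3 (total 1,490), the overall ranges are 0.79 to 3.14 and 1.99 to 7.94, so that discrepancy does not matter here.

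Chance of a true zero in all 1,470 women = exp(−expected deaths):

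| Share with a birth | At 211 | At 533 |
|---|---|---|
| 25% | 46% | 14% |
| 50% | 21% | 2% |
| 100% | 4.5% | under 0.1% |

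**Could a comparison work with full capture?** Take the most favourable case: one birth each, 0.533% in controls and half that, 0.2665%, in Chama women. By the two-proportion normal approximation, two-sided 5%, power is about 13% for 742 (142 + 600) against 728, and about 3% for 142 against 728. For 80% power, about 8,800 women per arm would be needed.

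**The case against.** **The survey form and field manual are not shown.** The December 2021 survey is said to have collected these outcomes, and a CHV looking for a woman may well learn that she has died. The form could also ask about deaths in the household. This is fair, and it is why the point is limited to what is described. But a question about other household members would not measure the cohort women's own risk, and recording at tracing would leave cohort 1 at zero. Who is surveyed and how the cohorts are formed are set in this protocol, and a later analysis plan cannot supply a missing data source.

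**The planned use is modest.** The analysis text never names maternal death, and its modelling examples are insurance and antenatal visits. This stands and limits the weight of the point. Still, the stated aim of understanding effects covers the whole outcome list.

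**Two stronger readings are not supported.**

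- A reader might infer that the cohort lists have already dropped deaths. The protocol says "Based on our total recruitment in the RCT (n = 1,550"), whereas the cohorts sum to 1,470 or 1,490, leaving 80 or 60 women in no cohort. But cohort 2 takes only women who left after 12 March 2020, so earlier leavers belong to no cohort by definition. The gap is not evidence of omitted deaths.
- A reader might infer that a reported zero would be false. A true zero is quite possible at the lower assumptions (46%). The fault is that the count cannot be interpreted.

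**Conclusion.** The point holds as a secondary-outcome defect. Followed as written, the protocol gives a maternal death count of zero in every cohort regardless of risk. If deaths came to light at tracing, cohort 1 would remain at zero by definition, and its comparison with cohorts 2 and 3 would favour continued participation. This is certain for cohort 1. For cohorts 2 and 3 it rests on the described survey being the only source.

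The 0.8 to 7.8 expected deaths in 1,470 women rest on the assumed birth share and on global and regional ratios, since no county ratio is given. They show scale only, but they are enough to rule out a useful cohort comparison even with complete ascertainment.

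The primary PPI outcome and its sample sizes are untouched. Newborn and infant deaths can be reported by surviving mothers, so they do not share the defect, apart from infants whose mothers died.

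**What to change.** Choose one before the survey starts.

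1. **Delete maternal death from the secondary outcomes.** This needs only a wording change. It gives up any information on deaths.
2. **Keep it with a source independent of the woman's interview.** At tracing, record vital status, date of death and relation to pregnancy for every listed woman, by one procedure for former intervention and control women. State how a woman who died while a Chama member is classed. Report deaths descriptively by original RCT allocation, with all listed women as the denominator and the number of unknown vital status shown. Do not compare cohort 1 with cohort 2.

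The second option adds three fields to the tracing record. It also requires a tracing procedure for control women, because the one described covers only women who took part in Chamas. It need not extend to RCT women outside the three cohorts. Its weakness is reliance on informants: reports may be incomplete, or differ between arms where CHVs know former Chama women better.
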